## 1. OBJECTIVES

### Primary

To determine the specificity and sensitivity of the blood based assay vis-à-vis tissue based BRAF analysis in patients with advanced and high-risk melanoma.

### Secondary

1. To explore the pharmacodynamic effects of MAPK pathway inhibitors (including selective BRAF inhibitors, MEK inhibitors, and ERK inhibitors) utilizing pre- and on-treatment peripheral blood BRAFV600E mutational testing in patients with advanced melanoma (non-resectable Stage III or Stage IV).
2. To define the prognostic value of peripheral blood BRAFV600 mutational testing in patients with Stage II and resectable Stage III melanoma.

### 1.1 Study Design

For the purposes of serum and plasma isolation optimization, patients who have agreed to participate in the study will donate no more than 20cc of peripheral blood (hereafter referred to as 1 sample) per timepoint. 10-20 ml blood will be acquired via standard venipuncture for serum and peripheral blood lymphocyte extraction at baseline and at varying intervals of time for each patient cohort. Amount of blood collected will follow the DF/HCC *Guidance for Maximum Blood Draw for Research Purposes*.

Any patient may refuse a research blood draw at any time while on study, or may refuse to continue donating samples at any time and may withdraw consent from participation. Subjects will receive no compensation for participation in this study. All unused collected blood will be saved for possible use in future related analyses.

### 1.2 Primary Objectives

To determine the sensitivity and specificity of peripheral blood BRAFV600 mutation detection in patients with melanoma, we will analyze samples from two distinct cohorts of patients: 1) Patients with advanced melanoma; and 2) Patients with resected, Stage II or Stage III disease. A total of 110 patients in each cohort will be recruited to participate. Peripheral blood lymphocytes (PBL) and serum will be isolated from blood. RNA will be isolated from tissue and PBL/serum and BRAFV600 analysis will be performed. Patients will be identified as being either positive or negative for the BRAFV600 mutation based on the results of the tissue testing. The tumor tissue (either primary tumor or nodal/systemic metastasis) from each patient with advanced disease, or from all patients with Stage II or resectable Stage III disease with adequate tissue, will be analyzed in a CLIA-approved laboratory for BRAFV600 sequencing analysis, either at the MGH TRL or at Clariant Laboratories using the FDA-approved Cobas® test. The results of the tissue-based and peripheral blood test will be compared and percent concordance will be determined.

### 1.3 Secondary Objectives

1. To explore the pharmacodynamic effects of MAPK-directed therapy on peripheral blood BRAFV600 mutation detection, we will test isolated PBL and serum from samples obtained from patients in the cohort with advanced melanoma prior to receiving treatment with MAPK-directed therapy or immunotherapy (either commercially or on protocol). Patients will have been previously identified as being positive for a BRAFV600 mutation based on the results of the testing of their tumor tissue. PBL and serum will be isolated from blood. RNA will then be isolated from tissue and PBL/serum and BRAFV600 analysis will be performed as described above. Peripheral blood samples obtained prior to each cycle of MAPK-directed therapy or immunotherapy (either every three weeks or every four weeks depending on treatment protocol) will also be tested for BRAFV600 RNA. Input RNA normalization will be carried out by using primers to a ribosomal protein, S-9, following the reverse transcription. Pre- and on-treatment BRAFV600 levels will be compared, and a blood-based response will be defined as a 50% or more decrease in signal based on acrylamide gel analysis. A blood-based progression will be defined as a doubling in signal based compared with nadir level on acrylamide gel analysis. A comparison of blood-based response or progression (  $\geq 50\%$  improvement vs.  $< 50\%$  improvement; or 100% increase vs.  $< 100\%$  increase) with clinical response (CR/PR by RECIST) and clinical progression (PD) will then be performed to assess concordance between changes over time with our assay and with imaging.
2. To explore the prognostic and predictive ability of peripheral blood BRAFV600 mutation detection in the cohort of patients with Stage II or resected Stage III disease, we will test isolated PBL and serum from samples obtained from patients following complete resection of their disease but prior to receiving adjuvant therapy or embarking on expectant monitoring. To control for potential variations in circulating BRAF levels at various post-operative time points, patients must have their blood draw at least 4 weeks but no more than 8 weeks following their last surgery. Additionally, all patients with a thick primary melanoma (defined by AJCC as Breslow depth greater than 4 mm) or a clinically apparent/macroscopic involved lymph node, satellite lesion, or in-transit lesion will have tissue-based BRAF analysis performed either at the MGH TRL, at Clariant Laboratories using the FDA-approved Cobas® test, or in MGH pathology using BRAFV600 stain. PBL and serum will be isolated from blood collected in two 10 mL green top tubes on each patient and will then be placed in Trizol Reagent prior to RNA isolation. RNA will then be isolated from tissue and PBL/serum and BRAFV600 analysis will be performed as described above.

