### 5. STUDY DESIGN

#### 5.1 Sample Collection

##### Advanced Disease Cohort:

Blood samples will be obtained on participants following signed informed consent. For patients in the advanced melanoma cohort, a one-time blood sample will be obtained prior to the commencement of systemic therapy at a time when standard-of-care blood will be drawn. While it is ideal to obtain samples prior to any systemic therapy, participants who have previously received therapy, have progressed, and are in need of additional therapy will be considered suitable for participation. Participants with known BRAF mutation (determined by standard of care tissue testing) will undergo blood draws every 4 weeks (+/- 1 week) and at the time of disease progression.

**BRAF WT (tissue):** One- time, pre-treatment blood draw

**BRAF Mut (tissue):** Pre-treatment blood draw then every 4 weeks (+/- 1 week). A

blood draw at time of progression will also be obtained.

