## 9. STATISTICAL CONSIDERATIONS

### 9.1 Study Design/Endpoints

**Primary Objective: To determine the sensitivity and specificity of the peripheral blood BRAFV600 mutation detection.**

Two cohorts of melanoma patients will be assessed using the blood-based assay: patients with advanced disease (non-resectable Stage III or Stage IV), and patients with Stage II and resectable Stage III disease. Assessments of diagnostic accuracy, such as sensitivity, specificity, and positive predictive value (PPV) of the blood-based assay, will be compared separately for the two cohorts, and will use paired binary data. Sample size estimates are based on the binomial distribution and joint 90% confidence regions for sensitivity and specificity to adjust for the two comparisons being performed. Positive and negative expression will be determined using optimized cut points for the assay that have already been established.

We are seeking evidence that the assay has the ability to detect both the presence of BRAF mutation in melanoma (sensitivity) and accurately indicate when a BRAF mutation is not present (specificity) in order to provide BRAF-directed therapy when indicated. We propose a sample of 110 patients with advanced melanoma to test the performance of the assay, and would require sensitivity of at least 0.80 and specificity of at least 0.90. We set our target sensitivity to be 0.90 and specificity to 0.95. With a sample size of 110 patients (approximately 55 with BRAF mutation and 55 without) and the assumed target sensitivity, the lower bound of the joint 90% confidence region will be greater than 0.82; the lower bound of the 90% joint confidence region for the specificity will be approximately 0.90.

We will also estimate the PPV of the assay to evaluate the practical utility of the test. Based on a sample size of 110 patients, Table 1 summarizes the estimated PPV and corresponding 90% confidence intervals over a range of prevalence rates of BRAF mutation, using the minimum and target levels of sensitivity and specificity. With a sample of 110 patients, the lower bound of the 90% confidence interval for PPV will be no less than 0.74.

Table 1 – Estimates of PPV and 90% Confidence Intervals

Prevalence Rate	Sensitivity	Specificity	PPV	90% Confidence Interval for PPV
0.4	0.80	0.90	0.84	(0.74 to 0.91)
	0.90	0.95	0.92	(0.83 to 0.97)
0.5	0.80	0.90	0.89	(0.80 to 0.94)

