## Secondary Objectives

### 1. Exploration of the pharmacodynamic effects of MAPK pathway inhibitors on pre- and on-treatment peripheral blood BRAFV600 mutational testing.

The exploration of pharmacodynamic effects will be based on the cohort of patients with advanced, BRAF-mutated disease confirmed by tissue analysis. We would expect that 50% of the cohort would have BRAF-mutated disease and that 90% of those patients will agree to participate in the pharmacodynamic studies. This results in a sample of size 50.

Our first investigation will correlate blood-assay results with pre-treatment radiographic measures of disease burden. We hypothesize that the cases with the lowest tumor burden would be most likely to have a negative blood assay result. We will use the sum of the longest diameter of tumor target lesions as the measure of disease burden using RECIST criteria (version 1.1). For this analysis, tumor burden will be a continuous outcome, and the blood assay will be classified as positive or negative. We will summarize baseline tumor burden descriptively and compare by assay result using the Wilcoxon rank-sum test. If the blood-assay is positive in 80% of the samples (N=40) and negative in 20% (N=10), a Wilcoxon-rank sum test, with a two-sided type-I error of 10%, will have 80% power to detect a difference in disease burden that is 0.95 times the common standard deviation.

The behavior of the blood-based assay with respect to early changes in disease will be assessed at the time of the first restaging. Since there are no prior data to suggest how assay levels will change in response to treatment, analyses will be primarily descriptive. Two analyses are proposed to explore the relationship between the performance of the assay and early clinical response. In both analyses, clinical response will be classified according to RECIST criteria (i.e., CR/PR vs. SD vs. PD vs. not assessable).

At the time of the first restaging, pre- and on-treatment blood-assay levels will be compared. Fold-changes in assay response will be calculated (post/pre). Fold-changes will be used as a continuous measure and will also be classified according to 0.5 or less (assay-based response), 2 or greater (assay-based progression) and between 0.5 and 2 (intermediate). Fold changes in the assay will be compared across RECIST responses using the Kruskal-Wallis test. In addition, for

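### The MAPK-inhibitor pharmacodynamic analysis admits immunotherapy patients without a split by therapy class, so its on-treatment results could not be read as a MAPK-inhibitor effect

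*Combined protocol and SAP*

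**What the plan says.** The objective (Section 1, Secondary, item 1) is drug-specific: "To explore the pharmacodynamic effects of MAPK pathway inhibitors (including selective BRAF inhibitors, MEK inhibitors, and ERK inhibitors". The heading of secondary objective 1 in Section 9.1 repeats MAPK pathway inhibitors, and the last paragraph of Section 2.3 states the aim in the advanced setting in the same terms.

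Section 1.3, item 1, which describes how the objective will be met, is wider. The baseline sample is taken "prior to receiving treatment with MAPK-directed therapy or immunotherapy (either commercially or on protocol". The on-treatment samples are described as: "Peripheral blood samples obtained prior to each cycle of MAPK-directed therapy or immunotherapy (either every three weeks or every four weeks depending on treatment protocol".

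Section 5.1 starts serial sampling on tissue BRAF status alone. Participants with a known mutation "will undergo blood draws every 4 weeks (+/- 1 week) and at the time of disease progression", whatever therapy they receive.

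Section 9.1 defines the analysis set without reference to therapy: "The exploration of pharmacodynamic effects will be based on the cohort of patients with advanced, BRAF-mutated disease confirmed by tissue analysis". Its size comes from the same definition: "We would expect that 50% of the cohort would have BRAF-mutated disease and that 90% of those patients will agree to participate", and then "This results in a sample of size 50".

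Section 9.1 also says that these analyses are primarily descriptive, because there are no earlier data on how assay levels change with treatment.

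**The concern.** A pharmacodynamic effect belongs to a drug class. If patients on immunotherapy are in the same fold-change distribution as patients on BRAF, MEK or ERK inhibitors, the summary depends on how many of each happened to enrol. It then does not estimate the quantity named in the objective.

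Therapy class may also be associated with RECIST category at first restaging. A pooled difference in fold change across RECIST categories could then partly reflect which class of drug was given. The reader of the final report would have no planned output from which to tell these apart, and a split made after the data are seen would carry less weight than one written down now.

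**Working it through.** **1. The plan's own sample size.** The inputs are the advanced cohort of 110, a 50% BRAF-mutant share and 90% participation, all from Section 9.1. 110 × 0.50 × 0.90 = 49.5, which rounds to the stated 50. The calculation has no factor for therapy class, so the 50 is the whole participating BRAF-mutant group, including anyone on immunotherapy.

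**2. The population, place by place.**

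| Place | Therapy covered |
|---|---|
| Section 1, secondary objective 1 | MAPK inhibitors only |
| Section 1.3, item 1, baseline and on-treatment samples | MAPK-directed therapy or immunotherapy |
| Section 5.1, serial draws | Any; set by tissue BRAF status |
| Section 9.1, heading of secondary objective 1 | MAPK inhibitors only |
| Section 9.1, analysis set and N | All advanced BRAF-mutant patients |

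Immunotherapy is named for both the baseline and the on-treatment samples in Section 1.3, so it is unlikely to be a slip.

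**3. Each on-treatment analysis in Section 9.1.**
- Fold change across RECIST categories (Kruskal-Wallis): no therapy factor.
- Proportions with CR/PR, SD or PD among assay-based responders or progressors, with exact 90% intervals: none.
- Spearman correlation of assay and tumour-burden fold changes: none.
- Four groups by assay status before treatment and at first restaging: none.
- Graphs over time: disease status and progression are marked, therapy is not.

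By contrast, the predictive analysis for the Stage II/III cohort (Section 9.1, Predictive Ability of the Assay) sorts treatment into four groups, with immunotherapy and BRAF/MEK inhibitors apart. It uses treatment group in the graphs and as a covariate in the models. Nothing equivalent is written for the advanced cohort.

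**4. What a pooled summary estimates.** Let f be the MAPK-treated share of the 50, and let p_M and p_I be the blood-response proportions on MAPK therapy and on immunotherapy. The pooled proportion is f × p_M + (1 − f) × p_I. It equals p_M only if f = 1 or p_I = p_M. The documents give none of the three quantities, so neither the size nor the direction of the difference from p_M can be stated.

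**5. The number that informs the MAPK question.** n = 50 × f, with f assumed:
- f = 0.9: 45
- f = 0.7: 35
- f = 0.5: 25

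**6. The powered test.** Section 9.1 claims 80% power for a rank-sum comparison of baseline tumour burden, 40 assay-positive against 10 assay-negative, for a difference of 0.95 SD at two-sided 10%. I used a noncentral t calculation with the group sizes multiplied by the minimum relative efficiency of the rank-sum test, 0.864:
- effective sizes: 40 × 0.864 = 34.56 and 10 × 0.864 = 8.64
- noncentrality: 0.95 / √(1/34.56 + 1/8.64) = 2.50
- power: 79.1%

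With efficiency 3/π the power is 82.7%, and simulation with normal data gives 82.4%. The stated figure reproduces. Both variables in this test are measured before treatment, so the therapy mix does not enter.

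**The case against.** The strongest reply is that Section 9.1 plans no test of the pooled fold change against one for this cohort. It compares assay change with imaging, and Section 1.3 gives concordance between the two as the purpose. Agreement between assay and imaging can be read across therapies. This stands, and it is why the pooled analysis should be kept for that use. It does not make the pooled result a MAPK-inhibitor effect, which is what the objective and the heading promise.

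Three further points stand in part:
- The work is exploratory and descriptive, so no confirmatory claim is at risk. The descriptive output still needs the population named in the objective.
- Pooling is inferred from the absence of any split; the plan does not announce it.
- Section 5.2 describes prospective enrolment around the use of BRAF inhibitors, so immunotherapy patients may be few. That is neither an eligibility rule nor an analysis rule, and Section 1.3 admits them expressly.

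The documents do not support some stronger readings that a reader might infer:
- *That a stated precision or power figure for this objective is wrong.* The planned exact intervals use subsets defined by assay result as denominators, not all 50. The bound of 0.25 on interval width belongs to the Stage II/III cohort. The only power figure for this objective is for the pre-treatment test.
- *That pooling must weaken the correlation between assay and tumour change.* If the two classes differ in their average change on both measures, the pooled correlation can be lower or higher than the one within the MAPK class.
- *That restricting to MAPK-treated patients would isolate the drug effect.* It would still be an uncontrolled before-and-after comparison. The restriction only matches the population to the objective.

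**Conclusion.** The concern holds as a mismatch between a MAPK-specific objective and an analysis set that admits immunotherapy, with no separation by therapy class in any on-treatment analysis. As written, those results would blend the two classes in an unknown proportion and could not support a MAPK pharmacodynamic conclusion.

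The reach is limited to the on-treatment part of one exploratory secondary objective. Its size cannot be fixed from the documents because f is not given; the 25 to 45 range rests wholly on the assumed f of 0.5 to 0.9. If no immunotherapy patient were enrolled (f = 1), the problem would not arise in practice, but nothing in the plan ensures that.

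**What to change.** In Section 9.1, secondary objective 1:
- Present every on-treatment analysis by therapy class, following the classification already used for the Stage II/III cohort. That scheme names BRAF/MEK inhibitors but not ERK inhibitors, which the objective includes, so state that ERK inhibitors count in the MAPK class.
- Make patients on a BRAF, MEK or ERK inhibitor the set for the MAPK pharmacodynamic conclusion.
- Report immunotherapy patients in parallel.
- Keep the pooled result only as overall assay-imaging concordance, labelled as such.
- Keep all 50 for the pre-treatment tumour-burden comparison.
- State that the MAPK-treated number will be 50 × f, with the expected f or a range for it.

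In Section 5.2, name therapy class as a data item. The current list covers demographics, coded encounters and clinic notes but no treatment field. The medical record is already the source, so the class should be obtainable from it.

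The cost is a wording change and one extra data field, with no added patients, blood draws or visits. The downside is smaller numbers in each class, and so less precise class-specific summaries.

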## **2. BACKGROUND**

### **2.1 Study Disease**

Metastatic melanoma is currently the 5th and 6th most common cancer in American men and women, respectively, and remains one of the few cancers with a rising incidence.(1) Over 9000 people are expected to die in the United States in 2012 from this dreaded disease. Recent treatment advances have been made which has led to the FDA approval of both vemurafenib, a BRAF inhibitor, and ipilimumab, an immunotherapy, for the treatment of patients with advanced

melanoma.(2-4) Unfortunately, the overwhelming majority of these patients still will die of their disease in spite of receiving these therapies.

## **2.2 IND Agent**

No therapeutics to be administered under this protocol

## **2.3 Rationale**

Strategies are underway to improve the effectiveness of BRAF-directed therapy and immune-based therapy, and similar efforts are needed to develop biomarkers with which we may better select treatment for melanoma patients and follow patients while they are being treated. With BRAF-targeted therapy now established as a standard therapy for metastatic melanoma, the development of highly-sensitive, blood-based assays have the potential to greatly improve the care of patients with BRAF-mutant melanoma in four major ways.

First, less than half of all patients with cutaneous melanoma have a tumor that harbors an oncogenic BRAF mutation.(5) In practice, current BRAF mutational analytic techniques are only capable of testing archival tissue and have limited sensitivity. Additionally, test results typically take two to three weeks, when factoring tissue acquisition and shipping issues, which delays the initiation of therapy for typically ill patients. Lastly, very often a patient who previously was diagnosed with an early stage melanoma who recurs will have a fine needle aspiration performed to confirm the diagnosis, and performing BRAF mutational analysis can be challenging due to the small amount of tissue that is obtained during such procedures. We believe that analyzing blood for the BRAF mutation will prove to be a more efficient method of determining a patient's BRAF status and possibly a more reliable one.

Second, tumor resistance to BRAF-directed therapy typically develops within six to eight months following initial tumor regression, but with a range of 2 months to 2 years.(2, 6-9) Importantly, each described mechanism involves the retention of the initiating BRAF mutation.(10-20) As the mechanisms of resistance are just now being elucidated, we feel that diagnostic assays which may identify developing resistance at an earlier time-point than standard clinical or radiographic assessments will have the ability to assist clinicians and researchers in determining the best next treatment option for patients whose disease is progressing on BRAF-directed therapy. This is particularly important due to the fact that a number of patients treated with BRAF inhibitors progress quite quickly following initial disease regression.(7) In these patients, it is typically difficult to transition to other therapies, such as ipilimumab, due to the rapid pace of growth in these resistant tumors.(21) While there is no current data which specifically supports such a strategy, it is thought that more advanced notice of disease progression when disease growth is more modest would allow for a more timely shift in treatment and improved benefit of next line therapy. Essentially, identifying a blood-based assay that can detect more subtle changes in disease burden than standard cross-sectional imaging would be requisite towards implementing this type of an approach. In addition, earlier detection of disease progression would also predictably allow investigators to analyze tumors or circulating tumor cells in these patients with a goal of determining the specific mechanism of resistance for an individual patient. This would have the added value of predicting which next therapy would be most appropriate for any

individual patient.

Third, over the next 12 months, it is expected that multiple trials will open to test the effectiveness of BRAF-directed therapy in patients with resected, high-risk disease. In patients with resected disease, the current standard of care for adjuvant therapy is interferon alpha, which has reproducibly been shown to improve disease-free survival but not overall survival.(22) Further, while the development of serologic or clinical evidence of autoimmunity has been associated with a marked improvement in overall survival in patients treated with adjuvant interferon, there has never been a reliable pre-treatment biomarker that predicts which patients are more likely to benefit from this therapy.(23) It is critical that trials of adjuvant BRAF-directed therapy test potential predictive biomarkers of benefit. One such biomarker would surely be a detectable BRAF mutation in tissue, as it is clear that patients with advanced melanoma only benefit from BRAF-directed therapy if they have a tumor with a detectable BRAF mutation, however assessment of BRAF mutations in primary melanoma samples may be complicated by substantial tumor heterogeneity.(24) This may lead to both more false negatives and false positives, as it may not be clear which of the heterogeneous clones will ultimately establish metastasis. While it is uncertain whether detectable or high levels of circulating BRAF will be prognostic of a poor outcome or predictive of benefit to adjuvant BRAF-directed therapy, it is critical to evaluate both the predictive and prognostic qualities of blood-based BRAF assays in patients enrolled in adjuvant trials of BRAF inhibitors, as it is more likely that circulating cells of the subpopulations of primary melanomas are more reflective of the cells that will recur.

Fourth, the recommended optimal follow up of patients who are currently rendered disease free with surgery for their melanoma is unknown. Namely, the current NCCN guidelines do not recommend any blood analysis for such patients and only concede that considerations be made towards routine imaging in patients with higher risk disease (stage IIB-resected stage IV).(25) The development and validation of a blood-based prognostic biomarker would offer the potential to improve these guidelines and potential help direct radiographic imaging. As an example, it is conceivable that the positive predictive value of cross-sectional imaging would be much higher in the context of a rising biomarker, much the way it is in patients with concerning symptoms, then when imaging is performed at randomly selected intervals.

[figure not shown]
In summary, a blood-based BRAF mutational analysis has the potential to:

1. Enhance and potentially replace tissue based BRAF mutation detection.
2. Detect disease progression at an earlier time-point than imaging which may improve the effectiveness of next line therapy (given the lower tumor burden), and mechanism of resistance analysis for patients with BRAF mutant disease progressing on BRAF-directed therapy.
3. Predict which patients respond to adjuvant, BRAF-directed therapy.
4. Serve as a prognostic biomarker for patients with resected melanoma that may be followed serially and help clinicians choose which patients to perform diagnostic imaging.

Mutational testing for BRAFV600 in tumor tissue has been well described using techniques such as bidirectional direct fluorescent sequencing and allele-specific polymerase chain reaction. The sensitivity of these assays, however is limited in that the assays in current use are only able to

detect the mutation if the tumor cells constitute >5-10% of the specimen submitted for genetic analysis.(26) While this degree of sensitivity is typically sufficient to detect the presence of the BRAF mutation in a homogenous tumor nodule, this is likely not sensitive enough to detect a few tumor cells in the background of a high percentage of stromal or lymphatic elements, infiltrating lymphocytes, or peripheral blood cells.

Recently, we have developed an RT-PCR-based technique that takes advantage of a unique restriction enzyme site present in wild-type (WT) but not the mutant BRAF to enrich the sample for the mutant form initially and then inserts a restriction site into the mutant but not WT BRAF to allow for detection and quantification of mutant BRAF.(27) As outlined in our original description of this technique and Figure 1, the protocol involves a series of PCR amplifications and restriction digestions that discriminate between WT and mutant BRAF at amino acid position 600. An initial RT-PCR is followed by digestion with TspR1 that preferentially digests the WT product but not the BRAFV600 PCR product. A nested PCR using the digested material follows. This PCR product is subjected to sequencing using a nested oligonucleotide. The PCR product is then subjected to a third PCR (product 140 bp) using a unique nested forward oligonucleotide that creates a Xba 1 restriction site in the amplified product only within the mutant sequence. After an Xba 1 digest, the products (108 and 32 bp) are separated on 15% acrylamide gels. After ethidium bromide staining the band at 108 bp is quantitated by densitometry.

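### The plan does not mask those who run and read the blood assay to tissue BRAF status, although that status can be known when the gel is read

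*Combined protocol and SAP*

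**What the plan says.** **Endpoint and readout.** Sections 1.2 and 9.1 compare the blood result with tissue BRAF status, which is the reference. Section 2.3 describes the blood readout, after the last digestion and gel separation: "After ethidium bromide staining the band at 108 bp is quantitated by densitometry".

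**How a call is made.** Section 9.1 states: "Positive and negative expression will be determined using optimized cut points for the assay that have already been established". No cut-point value is given. Section 2.3 names optimising the quantification as the next development step and says other ways of analysing the data are being explored.

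**Where tissue status enters the sampling.** In the advanced cohort (Section 5.1) tissue wild-type patients give a "One- time, pre-treatment blood draw". For the others: "Participants with known BRAF mutation (determined by standard of care tissue testing) will undergo blood draws every 4 weeks (+/- 1 week", with a further draw at progression. Section 1.3, item 1, says the patients in the pharmacodynamic analysis will already have been found mutation-positive on tissue. Section 5.1 also allows retrospective samples from two banking protocols.

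**Performance standard.** For the advanced cohort the plan "would require sensitivity of at least 0.80 and specificity of at least 0.90", and adds: "We set our target sensitivity to be 0.90 and specificity to 0.95".

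**Masking.** The protocol provides for no coded samples, masked operator, controlled run order or locking of blood calls. The nearest text, Section 5.2, keeps health information out of the research database. It protects privacy and does not separate the laboratory from the tissue result.

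**The concern.** When an index test is compared with a reference standard, whoever reads the index test should not know the reference result. If the operator knows that a patient is tissue-mutant, a faint band may be outlined more generously, background subtracted differently, or a negative run repeated. The opposite may happen for a wild-type patient. Moving a threshold trades sensitivity against specificity. Reading towards the known answer raises both, so the results themselves would not reveal it.

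At stake is the primary accuracy estimate in the advanced cohort, the only cohort with a performance requirement. The secondary comparison of gel-based response and progression with RECIST is exposed in the same way, because nothing masks the operator to imaging results.

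**Working it through.** **Step 1. When can tissue status be known?** What matters for reader bias is knowledge when the gel is read, not when blood is drawn.

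- *Advanced, serial samples:* known, because only tissue-mutant patients give them (Section 5.1).
- *Advanced, baseline samples:* sometimes known. Section 5.1 takes this sample before systemic therapy and does not make it wait for the tissue result, and Section 2.3 puts tissue turnaround at two to three weeks. But Section 1.3 describes the pharmacodynamic patients as already mutation-positive. Section 9.1 sizes that group at 50 (110 × 0.50 × 0.90 = 49.5), out of about 55 mutant patients.
- *Banked samples:* could be known, since they predate the assay run. Section 5.1 mentions them under the Stage II/III heading.
- *Stage II/III, prospective samples:* the schedule does not depend on tissue status, and some patients have no tissue result (Section 9.1).

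The documents do not say when gels are run relative to any of this.

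**Step 2. Reproduce the plan's precision figures.** Section 9.1 uses "joint 90% confidence regions for sensitivity and specificity" and assumes: "With a sample size of 110 patients (approximately 55 with BRAF mutation and 55 without) and the assumed target sensitivity". For a rectangular joint region each margin has confidence √0.90 = 0.9487. Two-sided, z = 1.949. The Wald lower bound is p − z·√(p(1−p)/55).

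| Quantity | Calculation | Result | Plan states |
|---|---|---|---|
| Sensitivity 0.90 | 0.90 − 1.949·√(0.90×0.10/55) | 0.821 | above 0.82 |
| Specificity 0.95 | 0.95 − 1.949·√(0.95×0.05/55) | 0.893 | about 0.90 |
| Half-width at p = 0.5 | 1.949·√(0.25/55) | 0.131 | ±0.13 (Stage II/III) |

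The figures reproduce. Masking changes none of these inputs, so no sample size or bound needs correcting.

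**Step 3. What is one call worth?** One call in 55 moves an estimate by 1/55 = 1.8 percentage points. By the same method:

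| Measure | Count | Estimate | Lower bound | Minimum |
|---|---|---|---|---|
| Sensitivity | 48/55 | 0.873 | 0.785 | 0.80 |
| Sensitivity | 49/55 | 0.891 | 0.809 | 0.80 |
| Specificity | 52/55 | 0.945 | 0.886 | 0.90 |
| Specificity | 53/55 | 0.964 | 0.914 | 0.90 |

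Any limit on a count has a deciding call. Here it lies close to the expected counts: at target these are 0.90 × 55 = 49.5 and 0.95 × 55 = 52.25. With exact (Clopper-Pearson) joint bounds the deciding pairs move up by one: 49 versus 50 (0.778 versus 0.801) and 53 versus 54 (0.875 versus 0.903).

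**Step 4. Illustration of bias (assumed values, not in the documents).** Take true sensitivity 0.85 and let knowledge of tissue status turn a fraction f of false negatives positive. Observed sensitivity is 0.85 + 0.15f, with the Step 2 lower bound:

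| f | Observed sensitivity | Lower bound |
|---|---|---|
| 0 | 0.850 | 0.756 |
| 0.10 | 0.865 | 0.775 |
| 0.25 | 0.8875 | 0.804 |
| 0.50 | 0.925 | 0.856 |

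Under this assumption a small effect leaves the bound below 0.80 and a larger one carries it over.

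**The case against.** **Positivity is not a free visual call.** The band is measured by densitometry and compared with a cut point described as already established. No equivocal category appears in the plan. This is a real safeguard and it limits the bias. It does not settle the matter: no value is given, quantification is still being optimised, and a fixed cut point still leaves band boundaries, background correction and repeat runs to the operator.

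**The baseline sample need not reveal status.** It is the only draw that wild-type advanced patients give, so it is the natural one for the accuracy comparison, and the tissue result may be pending when it is taken. A reader might infer from the schedule that status is known before every blood draw. The documents do not support that, and it does not hold for the prospective Stage II/III draws. What remains is that nothing stops the operator from knowing by the time the gel is read.

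**Section 2.3 is background.** It describes the technique and cites a source not available here. The supportable statement is that the plan does not provide for masking. It does not follow that the laboratory worked unmasked.

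**The RECIST comparison is mainly descriptive** (Section 9.1), so exposure there has less consequence.

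**Conclusion.** The point holds in a limited form: the plan leaves the primary comparison open to reader bias, and prevention is cheap. It is a worthwhile improvement, not evidence that the results will be biased.

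The size of any bias cannot be computed, because the documents give neither a rate of borderline bands nor the order of reading. What can be shown is sensitivity to single calls: 48 versus 49 of 55, and 52 versus 53 of 55, fall on opposite sides of 0.80 and 0.90. This rests on 55 patients per group, two-sided joint Wald bounds, and applying the minimum to the lower bound. Section 9.1 sizes the study on lower bounds but does not say outright that they decide success. If the point estimate decides, the deciding pair for specificity is 49 versus 50 of 55 (0.891 versus 0.909), further below the expected 52.25.

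A reader might also infer that modest bias alone would carry specificity past 0.90. Suppose specificity is 0.92 in clear cases and 10% of bands are equivocal. Calling those in line with tissue instead of at random moves specificity from 0.92×0.9 + 0.05 = 0.878 to 0.92×0.9 + 0.10 = 0.928. The estimate crosses 0.90, but its joint lower bound is 0.860 and does not. Starting from the target of 0.95, the values are 0.905 and 0.955, with no crossing by the estimate. These inputs are assumed, so that inference is unsupported.

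**What to change.** Add to Section 5.1:

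- Blood samples go to the laboratory under a study code only. The code should be per sample: a patient number that recurs would itself show that an advanced patient is tissue-mutant.
- Baseline samples from tissue-mutant and wild-type patients are run in mixed batches. Wild-type patients have no later samples, so on-treatment samples are protected by the code and by locking.

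Add to Section 9.1:

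- The numerical cut point and the repeat-run rule, fixed before study samples are read.
- Densitometry values and positive/negative calls are locked before tissue status or RECIST response is merged.

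The cost is labelling and batch planning, with slightly slower turnaround because baseline samples wait for a batch. No extra patients, readers or tests are needed.
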